15.3.5 Immune-related adverse events

Based on the mechanism of action of durvalumab leading to T-cell activation and proliferation, there is a possibility of observing irAEs during the conduct of this study. Potential irAEs may be similar to those seen with the use of ipilimumab, BMS-936558 (anti-PD-1 mAb), and BMS-936559 (anti-PD-L1 mAb) and may include immune-

mediated enterocolitis, dermatitis, hepatitis (hepatotoxicity), pneumonitis, and endocrinopathies). Error! Bookmark not defined.¹ These AEs are inflammatory in nature and can affect any organ. Patients should be monitored for signs and symptoms of irAEs. In the absence of an alternate etiology (e.g., infection or PD), an immune-related etiology should be considered for signs or symptoms of enterocolitis, dermatitis, pneumonitis, hepatitis, and endocrinopathy. In addition to the dose modification guidelines provided in Appendix 1, it is recommended that irAEs are managed according to the general treatment guidelines outlined for ipilimumab. These guidelines recommend the following:

- Patients should be evaluated to identify any alternative etiology.
- In the absence of a clear alternative etiology, all events of an inflammatory nature should be considered immune related.
- Symptomatic and topical therapy should be considered for low-grade events.
- Systemic corticosteroids should be considered for a persistent low-grade event or for a severe event.
- More potent immunosuppressives should be considered for events not responding to systemic steroids (e.g., infliximab or mycophenolate).
- If the Investigator has any questions in regards to an AE being an irAE, the Investigator should immediately contact the PI.

15.3.6 Potential drug-induced liver injury

The combination of increased transaminases plus increased total bilirubin may be indicative of drug-induced liver injury (DILI), and should be considered as clinically important events. Patients meeting any of the following criteria will require further follow-up as outlined below:

- For patients with normal ALT, AST, and total bilirubin value at baseline: AST or ALT $> 3.0 \times$ ULN combined with total bilirubin $> 2.0 \times$ ULN.
- For patients with elevated AST, ALT, or total bilirubin value at baseline: AST or ALT $> 2 \times$ baseline and $> 3.0 \times$ ULN OR AST or ALT $> 8.0 \times$ ULN, whichever is lower, combined with total bilirubin $> 2 \times$ baseline and $> 2.0 \times$ ULN.

Medical review needs to ensure that liver test elevations are not caused by cholestasis, defined as an alkaline phosphatase elevation $> 2.0 \times$ ULN with R value < 2 in patients without bone metastasis, or elevation of alkphos liver fraction in patients with bone metastasis.

Note: The R value is calculated by dividing the ALT by the alkphos, using multiples of the ULN for both values [R value = (ALT/ULN)/(alkphos/ULN)]. It denotes the relative pattern of ALT and/or alkphos elevation is due to cholestatic or hepatocellular liver injury or mixed type injury.

An R value > 5.0 is used to define hepatocellular injury, R < 2.0 as cholestatic injury, and R between 2.0 to 5.0 as mixed hepatocellular-cholestatic injury.

In the absence of cholestasis, these patients should be immediately discontinued from study drug treatment, and repeat LFT testing as soon as possible, preferably within 48 hours from the awareness of the abnormal results. The evaluation should include laboratory tests, detailed history, physical assessment and the possibility of liver metastasis or new liver lesions, obstructions/compressions, etc.

All cases confirmed on repeat testing meeting the laboratory criteria defined above, with no other alternative cause for LFT abnormalities identified, should be considered as “medically significant”, thus met the definition of SAE, and reported as SAE using the term “potential drug-induced liver injury”. All events should be followed up with the outcome clearly documented.

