Hepatic function abnormality is defined as any increase in ALT or AST to greater than $3 \times$ ULN and concurrent increase in total bilirubin to be greater than $2 \times$ ULN. Concurrent findings are those that derive from a single blood draw or from separate blood draws taken within 8 days of each other. Follow-up investigations and inquiries will be initiated

promptly by the investigational site to determine whether the findings are reproducible and/or whether there is objective evidence that clearly supports causation by a disease (e.g., cholelithiasis and bile duct obstruction with distended gallbladder) or an agent other than the IP. Guidelines for management of patients with hepatic function abnormality are provided in Appendix 1.

Gastrointestinal disorders

Diarrhea/colitis is the most commonly observed treatment emergent SAE when tremelimumab is used as monotherapy. In rare cases, colon perforation may occur that requires surgery (colectomy) or can lead to a fatal outcome if not properly managed. Guidelines on management of diarrhea and colitis are provided in Appendix 1.

Endocrine disorders

Immune-mediated endocrinopathies include hypophysitis, adrenal insufficiency, and hyper- and hypothyroidism. Guidelines for the management of patients with immune-mediated endocrine events are provided in Appendix 1.

Pancreatic disorders

Immune-mediated pancreatitis includes autoimmune pancreatitis, and lipase and amylase elevation. Guidelines for the management of patients with immune-mediated pancreatic disorders are provided in Appendix 1.

Neurotoxicity

Immune-mediated nervous system events include encephalitis, peripheral motor and sensory neuropathies, Guillain-Barré, and myasthenia gravis. Guidelines for the management of patients with immune-mediated neurotoxic events are provided in Appendix 1.

Nephritis

Consult with Nephrologist. Monitor for signs and symptoms that may be related to changes in renal function (e.g. routine urinalysis, elevated serum BUN and creatinine, decreased creatinine clearance, electrolyte imbalance, decrease in urine output, proteinuria, etc)

Patients should be thoroughly evaluated to rule out any alternative etiology (e.g., disease progression, infections, etc.).

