15.5.2 Hepatic function abnormality

Hepatic function abnormality (as defined in section 15.4.6) in a study subject, with or without associated clinical manifestations, is required to be reported as "hepatic function abnormal" **within 24 hours of knowledge of the event** to the Principal Investigator, the PMC (via the RCO), and AstraZeneca/MedImmune Patient Safety using the designated Safety e-mailbox (see Section 15.5 for contact information), unless a definitive underlying diagnosis for the abnormality (e.g., cholelithiasis or bile duct obstruction) that is unrelated to investigational product has been confirmed.

Protocol name: DURVALUMAB TRIAL IN POSTMENOPAUSAL BREAST CANCER

Version Date: January 30, 2019

Principal Investigator: [name]

Version number: v5.1

- If the definitive underlying diagnosis for the abnormality has been established and is unrelated to investigational product, the decision to continue dosing of the study subject will be based on the clinical judgment of the investigator.
- If no definitive underlying diagnosis for the abnormality is established, dosing of the study subject must be interrupted immediately. Follow-up investigations and inquiries must be initiated by the investigational site without delay.

Each reported event of hepatic function abnormality will be followed by the investigator and evaluated by the Principal Investigator, the PMC, and AstraZeneca/MedImmune.

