Grade 3 or 4 (Grade 3: AST or ALT $>5.0 \times \text{ULN}$ and $\leq 20.0 \times \text{ULN}$ and/or TB $>3.0 \times \text{ULN}$ and $\leq 10.0 \times \text{ULN}$) (Grade 4: AST or ALT $>20 \times \text{ULN}$ and/or TB $>10 \times \text{ULN}$)	
For Grade 3:
 
For elevations in transaminases $\leq 8 \times \text{ULN}$, or elevations in bilirubin $\leq 5 \times \text{ULN}$:
 
 • Hold study drug/study regimen dose until resolution to Grade ≤ 1 or baseline • Resume study drug/study regimen if elevations downgrade to Grade ≤ 1 or baseline within 14 days and after completion of steroid taper. • Permanently discontinue study drug/study regimen if the elevations do not downgrade to Grade ≤ 1 or baseline within 14 days 	
For Grade 3 or 4:
 
 – Promptly initiate empiric IV methylprednisolone at 1 to 4 mg/kg/day or equivalent. – If still no improvement within 3 to 5 days despite 1 to 4 mg/kg/day methylprednisolone IV or equivalent, promptly start treatment with immunosuppressive therapy (i.e., mycophenolate mofetil). Discuss with study physician if mycophenolate is not available. Infliximab should NOT be used. – Perform hepatology consult, abdominal workup, and imaging as appropriate. – Once the patient is improving, gradually taper steroids over ≥ 28 days and consider prophylactic antibiotics, antifungals, and anti-PJP treatment (refer to current NCCN guidelines for treatment of cancer-related infections [Category 2B recommendation]).^a

For elevations in transaminases $>8 \times$ ULN

or elevations in bilirubin $>5 \times$ ULN,
discontinue study drug/study regimen.

Permanently discontinue study drug/study regimen for any case meeting Hy's law criteria (AST and/or ALT $>3 \times$ ULN + bilirubin $>2 \times$ ULN without initial findings of cholestasis (i.e., elevated alkaline P04) and in the absence of any alternative cause.^b

For Grade 4:

Permanently discontinue study drug/study regimen.

Nephritis or renal dysfunction	Any Grade	General Guidance	For Any Grade:

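### Sections 15.3.4, 15.3.6, 15.5.2 and the Appendix give conflicting triggers and dosing actions for a combined transaminase and bilirubin rise in identifiable cases

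*Combined protocol and SAP*

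**What the plan says.** Four places in the combined protocol and SAP deal with the same laboratory picture.

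- **Section 15.3.4 (adverse events of special interest)** supplies the term: "Hepatic function abnormality is defined as any increase in ALT or AST to greater than" 3 × ULN, together with total bilirubin above 2 × ULN. The limits are fixed. Blood draws up to 8 days apart count as concurrent.
- **Section 15.3.6 (potential drug-induced liver injury)** uses the same limits for patients with normal baseline values: "AST or ALT $> 3.0 \times$ ULN combined with total bilirubin $> 2.0 \times$ ULN". If any of the three tests is elevated at baseline, the transaminase limit becomes "AST or ALT $> 2 \times$ baseline and $> 3.0 \times$ ULN OR AST or ALT $> 8.0 \times$ ULN, whichever is lower", and the bilirubin limit becomes "total bilirubin $> 2 \times$ baseline and $> 2.0 \times$ ULN". Cholestasis is "defined as an alkaline phosphatase elevation $> 2.0 \times$ ULN with R value < 2 in patients without bone metastasis". When cholestasis is absent, "these patients should be immediately discontinued from study drug treatment, and repeat LFT testing as soon as possible". An alternative cause enters only afterwards, when deciding whether a confirmed case is an SAE.
- **Section 15.5.2 (hepatic function abnormality)** requires a 24-hour report, unless a definitive diagnosis unrelated to the product has been confirmed. On dosing it says: "If no definitive underlying diagnosis for the abnormality is established, dosing of the study subject must be interrupted immediately". If a definitive diagnosis unrelated to the product is established, continuing is for the investigator to judge. Its trigger is defined by reference to Section 15.4.6.
- **Section 18, Appendix (hepatitis, Grade 3 or 4)** stops treatment permanently for Hy's law cases at 3 × and 2 × ULN. The case must show no initial cholestasis, described only as an elevated alkaline phosphatase (ALP), "and in the absence of any alternative cause". The same table has separate hold and stop rules by grade.

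**The concern.** A site can comply with one of these sections and depart from another for the same patient on the same day. The protocol itself treats combined transaminase and bilirubin elevation as clinically important, so this is a poor place for ambiguity. Three things are at stake: whether drug is stopped, held or left to judgment; which patients are reported within 24 hours; and whether the study's two centers handle and record such cases alike.

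**Working it through.** No power or error-rate figure is involved. The check sets the rules side by side and applies the written thresholds. The patient values below are assumed for illustration; they are not from the documents.

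**Step 1. Actions and cholestasis definitions.** R = (ALT/ULN)/(ALP/ULN), as defined in Section 15.3.6.

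| Case (multiples of ULN) | 15.3.6 | 15.5.2 | Appendix, hepatitis |
|---|---|---|---|
| A. Normal baseline; ALT 6, bilirubin 2.5, ALP normal; no diagnosis yet | Discontinue, retest | Interrupt | At least a hold; permanent stop if no alternative cause |
| B. As A, but an unrelated, non-cholestatic diagnosis is established | Discontinue | Investigator's judgment | Hy's law stop does not apply; other hold or stop rules may |
| C. As A, but ALP 1.5 | R = 6/1.5 = 4.0, and ALP is not above 2: not cholestasis, so discontinue | Interrupt | ALP elevated, so Hy's law stop does not apply; Grade 3 row for transaminases ≤ 8 holds, with resumption possible after improvement within 14 days and steroid taper |

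Case A points the same way throughout. What differs is permanence: Section 15.3.6 says discontinued without saying permanently, Section 15.5.2 says interrupted, and the Appendix says permanently, subject to its conditions. Cases B and C are contradictions in the wording.

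**Step 2. Triggers when baseline is elevated.** Eligibility criterion 5.1.9 admits AST/ALT up to 2.5 × ULN and bilirubin up to 1.5 × ULN, with confirmed Gilbert's syndrome exempt from the bilirubin limit. With baselines a and c in multiples of ULN, the Section 15.3.6 limits are:

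- transaminase: min(max(2a, 3), 8)
- bilirubin: max(2c, 2)

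| Baseline AST/ALT | 15.3.6 limit | 15.3.4 and Appendix limit |
|---|---|---|
| 1.5 or less | max(3.0, 3) = 3 | 3 |
| 2.0 | max(4.0, 3) = 4 | 3 |
| 2.5 | max(5.0, 3) = 5 | 3 |

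| Baseline bilirubin | 15.3.6 limit | 15.3.4 and Appendix limit |
|---|---|---|
| 1.0 | max(2.0, 2) = 2 | 2 |
| 1.5 | max(3.0, 2) = 3 | 2 |

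The 8 × ULN arm never binds at an eligible baseline, because 2 × 2.5 = 5.

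Case D: baseline ALT 2.5 and bilirubin 1.5; on study, ALT 4 and bilirubin 2.5. Section 15.3.4 is met (4 > 3 and 2.5 > 2), and so are the Appendix's 3 and 2 limits. Section 15.3.6 is not met (4 < 5 and 2.5 < 3).

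**Step 3. The cross-reference.** The body has no Section 15.4.6. The contents list places Adverse Events at 15.4, whereas the body places it at 15.3, so by number the reference leads to current 15.3.6. By term it leads to 15.3.4, where hepatic function abnormality is defined. Whether Case D meets the trigger for the 15.5.2 report and interruption depends on which route the reader takes.

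**Step 4. Precedence.** Section 4.6.1, item 5, sends the reader to Section 10.3 and the Appendix for discontinuation criteria. Section 10.3 holds only the DLT pointer and the two-stage efficacy rule. No section says which liver rule prevails.

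**The case against.** The strongest reply is that the sections form a sequence: stop, retest and investigate, then make the stop permanent if no other cause is found. That reading fits Case A, although the protocol never states it. It does not settle Case B, where the cause is already known, nor Case C, where the two definitions of cholestasis disagree.

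A second reply is that the definitions serve different reports: a broad 24-hour alert in Section 15.5.2, and a narrower SAE in 15.3.6 confirmed on repeat testing. That is a fair reason for different reporting sets. It does not explain different dosing instructions, because the 15.3.6 stop comes before confirmation.

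A third is scope. Section 15.3.4 says the Appendix guidelines apply to events the investigator considers causally related, and Sections 4.6.1 and 7.1.2 send dosing decisions there. That narrows the overlap but does not override the instruction in 15.3.6. The unrelated diagnoses that Section 15.5.2 gives as examples are also biliary, and some would count as cholestasis under 15.3.6. The conflict in Case B is confined to causes that would not.

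The stale section number is clerical; the same shift appears in Sections 4.2, 6.4 and 7.1.2. It matters more here because it supplies a trigger.

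Three stronger readings might be inferred, and the documents do not support them:

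- **That some section keeps a patient on drug with no diagnosis and no cholestasis.** None does. The judgment branch of 15.5.2 requires a definitive diagnosis unrelated to the product.
- **That the Appendix stops permanently only when there is no alternative cause.** That condition belongs to the Hy's law sentence. The table also stops treatment for transaminases above 8 × ULN, bilirubin above 5 × ULN, Grade 4, and lesser Grade 3 elevations that have not downgraded within 14 days.
- **That every value between 3 and 5 × ULN is handled differently.** That is the widest gap, reached only at the eligibility ceiling. Within it, the Appendix Grade 2 row already holds drug for events in its scope, so a different classification is not shown to mean continued dosing.

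**Conclusion.** The inconsistency is real and limited. It consists of:

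1. discontinuation against investigator's judgment when an unrelated, non-cholestatic diagnosis is established;
2. two definitions of cholestasis, so that a mildly raised ALP leads to discontinuation under one and possibly only a hold under the other;
3. triggers that diverge for baseline AST/ALT above 1.5 and up to 2.5 × ULN (at most 3 versus 5 × ULN), and for baseline bilirubin above 1 × ULN (2 versus 3 × ULN at the 1.5 × ULN limit);
4. an invalid reference that leaves open which definition governs the 24-hour report and the interruption.

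Item 2 assumes that elevated ALP in the Appendix means any value above normal, since no threshold is given there. The documents give no event rate, so the number affected among up to 46 patients is unknown and may be small.

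The consequence is for consistency of safety conduct and reporting. A reader might infer that the efficacy result is at risk, but the documents do not support that. The efficacy set and the extension-phase safety set need only first dosing, so stopping drug does not remove a patient from them, and the two-stage design figures do not depend on these rules.

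**What to change.** Reconcile Sections 15.3.4, 15.3.6, 15.5.2 and the Appendix so that the trigger, the definition of cholestasis and the sequence of actions agree, including whether each stop is temporary or permanent. Alternatively, state which section prevails. If a broad alert and a narrower SAE definition are both intended, say so, and attach the dosing instruction to one of them. Replace the reference to 15.4.6 in Section 15.5.2 with the section whose definition is meant, and correct the pointer to Section 10.3 in Section 4.6.1.

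Which trigger and which action to adopt is a clinical decision for the sponsor and drug supplier; this review takes no position on it. The cost is amendment wording. Sample size and analysis do not change.

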15.4 SAE Reporting Requirements

SAEs must be reported concurrently to the IRB according to IRB policy and AstraZeneca within 24 hours of learning of the event.

All SAEs will be reported to the Clinical Trial Office of Moffitt Cancer Center in 24 hours via ONCORE.

External sites should abide by local IRB requirements for submission of SAEs.

AstraZeneca Notifications:

All SAEs will be reported, whether or not considered causally related to the investigational product, or to the study procedure(s). The reporting period for SAEs is the period immediately following the time that written informed consent is obtained through 90 days after the last dose of durvalumab or until the initiation of alternative anticancer therapy. The investigator and/or Sponsor are responsible for informing the Ethics Committee and/or the Regulatory Authority of the SAE as per local requirements.

The Investigator (or other designated site personnel) must notify the appropriate AstraZeneca representative of an SAE **no later than 24 hours after becoming aware of the event.**

The designated AstraZeneca representative will work with the Investigator to ensure that all necessary information is provided to the AstraZeneca Patient Safety data entry site **within 1 calendar day** of initial receipt for fatal and life threatening events and **within 5 calendar days** of initial receipt for all other SAEs.

For fatal or life-threatening adverse events where important or relevant information is missing, active follow-up is undertaken immediately. Investigators or other site personnel inform AstraZeneca representatives of any follow-up information on a previously reported SAE **no later than 24 hours** of becoming aware of it.

A MedWatch 3500A form must be completed along with a cover page indicating the following:

- “Notification from an Investigator Sponsored Study”
- The investigator IND number assigned by the FDA
- The investigator’s name and address

- The trial name/title and AstraZeneca ISS reference number (ESR-17-13182)

The investigator must also ensure that either the SAE report or the cover page detail the causality of the event in relation to all study medications and whether the event is related to disease progression, as determined by the principal investigator.

SAE reports and accompanying cover pages will be sent via email to AstraZeneca's designated mailbox: [contact]

If a non-serious AE becomes serious, this and other relevant follow-up information must also be provided to AstraZeneca and the FDA.

Serious adverse events that do not require expedited reporting to the FDA still need to be reported to AstraZeneca preferably using the MedDRA coding language for serious adverse events. This information should be reported on a monthly basis and under no circumstance less frequently than quarterly.

15.5 Other events requiring reporting

15.5.1 Overdose

An overdose is defined as a subject receiving a dose of durvalumab in excess of that specified in the Investigator's Brochure, unless otherwise specified in this protocol.

Any overdose of a study subject with durvalumab, with or without associated AEs/SAEs, is required to be reported **within 24 hours of knowledge of the event** to the Principal Investigator, the PMC (via the RCO), and AstraZeneca/MedImmune Patient Safety or designee using the designated safety e-mailbox (see Section 15.5 for contact information).

If the overdose results in an AE, the AE must also be recorded as such. Overdose does not automatically make an AE serious, but if the consequences of the overdose are serious, for example death or hospitalization, the event is serious and must be recorded and reported as an SAE.

There is currently no specific treatment in the event of an overdose of durvalumab. The investigator will use clinical judgment to treat any overdose.

15.5.2 Hepatic function abnormality

Hepatic function abnormality (as defined in section 15.4.6) in a study subject, with or without associated clinical manifestations, is required to be reported as "hepatic function abnormal" **within 24 hours of knowledge of the event** to the Principal Investigator, the PMC (via the RCO), and AstraZeneca/MedImmune Patient Safety using the designated Safety e-mailbox (see Section 15.5 for contact information), unless a definitive underlying diagnosis for the abnormality (e.g., cholelithiasis or bile duct obstruction) that is unrelated to investigational product has been confirmed.

Protocol name: DURVALUMAB TRIAL IN POSTMENOPAUSAL BREAST CANCER

Version Date: January 30, 2019

Principal Investigator: [name]

Version number: v5.1

- If the definitive underlying diagnosis for the abnormality has been established and is unrelated to investigational product, the decision to continue dosing of the study subject will be based on the clinical judgment of the investigator.
- If no definitive underlying diagnosis for the abnormality is established, dosing of the study subject must be interrupted immediately. Follow-up investigations and inquiries must be initiated by the investigational site without delay.

Each reported event of hepatic function abnormality will be followed by the investigator and evaluated by the Principal Investigator, the PMC, and AstraZeneca/MedImmune.

